7.7 HIV-RNA, CD4, CDC Classification, Time-course of Body Weight and Tropism

Date of test, number of HIV-RNA copies, CD4 count, CDC classification, body weight and tropism

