7.10 Priority Investigation Items

In this survey, the occurrence of the following items will be defined as the priority investigation items:

(i) Effect on immune competence

[Reason for selection]

Nonclinical or clinical studies of Celsentri have not suggested that Celsentri treatment increases infections, malignancies, etc. However, there is a concern that Celsentri may affect immune competence (onset of infections, malignancies, etc.) based on its mechanism of action to inhibit CCR5 chemokine receptors.

[Investigation method]

By focusing on the onset of AEs such as infections and malignancies, they will be tabulated by the causal relationship with Celsentri and stratified according to patient background characteristics to evaluate the safety of Celsentri.

(ii) Effect on liver function

[Reason for selection]

No clinical data obtained so far shows the effect of Celsentri on liver function compared with placebo. However, a nonclinical study in rats revealed high exposure to the liver. CCI

Also, a Phase III study of Celsentri (A4001026) reported cases of liver disorder suspected to be related to maraviroc and resulted in liver transplantation.

[Investigation method]

By focusing on the onset of abnormal liver function test values and AEs mainly corresponding to hepatobiliary disorders according to the System Organ Class (SOC) of the MedDRA, they will be tabulated by the causal relationship with Celsentri and stratified according to patient background characteristics to evaluate the safety of Celsentri.

(iii) Effect on the cardiovascular system

[Reason for selection]

Clinical studies and a Phase IIb/III study to evaluate QT prolongation revealed no clinically significant effect on the QTc interval. In addition, the onset of myocardial infarction and ischemic heart disease during Celsentri treatment is rare, and their incidence is the same as that in this population with a history of treatment. However, nonclinical studies suggested that Celsentri might prolong the QT interval at concentrations above the therapeutic concentration.

[Investigation method]

By focusing on AEs mainly corresponding to cardiac disorders according to the SOC of the MedDRA, they will be tabulated by the causal relationship with Celsentri and stratified according to patient background characteristics to evaluate the safety of Celsentri.

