8.2 Analysis Methods

(1) Analyses related to safety evaluation

In the safety analysis set, the primary analysis items will be the occurrence of common ADRs and the incidence of ADRs (proportion of patients with AEs with which Celsentri's causal

relationship could not be denied). In addition, when tabulating the incidence of ADRs by factor such as patient background characteristics, factors affecting the onset of ADRs will be also examined.

(2) Analyses related to efficacy evaluation

Efficacy parameters for anti-HIV drugs such as a CD4 count, number of HIV-RNA copies and CDC classification will be tabulated and analyzed by patient background characteristic to examine factors affecting the efficacy of Celsentri. In patients tested for tropism, the relationship with the status of tropism change will be also evaluated.

9. Organization System for the Implementation of the Survey

The survey will be conducted using the system described in Appendix 3 in accordance with the procedures for the implementation of the HRD cooperative investigation (Appendix 2). The procedures for notifying ADRs, etc. are presented in Appendix 4.

This survey will be performed as a cooperative investigation by companies marketing drugs for the treatment of HIV infection^{Note 1)} using a common CRF. The common CRF for the drug use-results survey may be completed one copy for one patient even if a few anti-HIV infection drugs are coadministered during the reexamination period.

10. Name and Address of the Contractee, and the Scope of the Concerned Outsourced Activities

(1) Contractee

Address: PPD [redacted]

Name: PPD [redacted], PPD [redacted] CMIC PMS Co., Ltd.

Name of the person responsible for implementation: PPD [redacted], Postmarketing Surveillance Operation Implementation Supervisor

(2) Scope of outsource activities

- 1) Request to and contract with institutions
- 2) Issuance of a user's ID and password to each investigator
- 3) Retention of the originals of enrollment forms
- 4) Sending the copies of enrollment forms
- 5) Verification of registration and investigation items entered and sent by the investigators
- 6) Collection of the originals of CRFs
- 7) Preparation and collection of the statement of confirmation
- 8) Sending the copies of CRFs
- 9) Arranging reinvestigation items
- 10) Request for a reinvestigation
- 11) Retention of the originals of CRFs
- 12) Sending the CRFs (final version)
- 13) Data locking
- 14) Coding
- 15) Data tabulation/analyses

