*A list of adverse reactions per patient background, etc.	Prepare a list for adverse reactions in <General Definitions>. © Displayed items: No., patient registration number, age, pediatrics, the elderly, race, presence/absence of pregnancy, presence/absence of complications, haemophilia, renal disorder, hepatitis A, hepatitis B, hepatitis C, others, liver disorder, syphilis, others, presence/absence of haemophilia, presence/absence of liver disorder, presence/absence of renal disorder, name of complication, presence/absence of allergy, presence/absence of concomitant treatment, name of concomitant treatment, presence/absence of concomitant drugs, number of concomitant drugs, presence/absence of concomitant anti-HIV drugs, number of concomitant anti-HIV drugs, administration period, long-term administration, presence/absence of adverse events, presence/absence of adverse reactions, name of adverse reactions (PT), seriousness, outcome, days to the onset, relationship with CELSENTRI
Incidence of adverse reactions per patient background	Prepare a table of incidence of adverse reactions on the following patient-background items: Follow the above <<Handling of Items>> for the definitions of each item per background. © Displayed items: primary disease, sex, presence/absence of pregnancy, age, inpatient/outpatient classification, treatment history of HIV infection, race, route of transmission, duration of disease, medical history, allergy, complication, type of complication, renal disorder, liver disorder, the mean daily dose, administration period, administration period [cumulative], total dose, total dose [cumulative], continued/discontinued, concomitant drug, number of concomitant drugs, type of concomitant drugs, number of concomitant anti-HIV drugs, type of concomitant anti-HIV drugs, presence/absence of CYP3A inducer, presence/absence of haemophilia, haemophilia AB, CDC classification of severity prior to administration, tropism classification at the first administration, concomitant treatment, blood coagulation factor (all cases and the cases with haemophilia) Calculate the minimum and the maximum for age, duration of disease, the mean daily dose, administration period, total dose while calculate the

	mean and the standard deviation for age as well (Of note, as to the description age for example, calculate the age of a patient in his 30s will be calculated as 30 years old).

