In the list of *, use a row for an adverse reaction; enter multiple adverse reactions in the equivalent number of rows for a patient. Entry of a patient number, etc. should be repeated.

4) Table for “Patients in the efficacy analysis group”

A table and a chart of changes in HIV-RNA load/CD4	
Prepare a chart and table on the changes in HIV-RNA load/CD4 in patients with and without treatment history, with and without concomitant CYP3A inhibitors, sex, with and without complications, with and without concomitant drugs, CDC classification and for all patients in the efficacy analysis group.
 
Pre-administration (Month 0) should be the most recent date within 30 days before administration including the first administration date.
 
For post-administration (Month 3, 6, 9, etc.), choose the value obtained on the most recent date within ±45 days from each point of Month 3, 6, 9, etc. If a “test value” is missing either before or after administrations, it should not be included in the chart.
 
Use a line chart with test values on the y-axis and months after administration (for every 3 months) on the x-axis.
 
For each point, extend the whisker in a single direction to show the SD value.
 
When you have n=1 for each point, display it with a dot without connecting it with a line.
 
Of note, for the maximum number of HIV-RNA copies detected, replace it with 399 from the initiation of survey to March, 2008, with 39 from April, 2008 to 2010 and with 19 in and after 2011 (depends on the site). Handle the encoded values, etc. as follows: Replace the values with inequality sign with the following [1] to [3] in calculation:

--	--

	
[1] <400: The value that you subtract 1 from the figure without inequality sign. Note that the inequality sign must be removed from the figures with inequality sign. For example: change "<20" to "19", "<40" to "39", "≤20" to "20", "≤40" to "40"
 
[2] ≥400 and <100000: Missing
 
[3] ≥100000: the value without inequality sign. For integer values less than 400 with no inequality sign, use them as they are without replacement.

Patients included in the chart [data in each plot]	Display the patient registration numbers and test results for each point of Month 0, 3, 6, 9, etc. to the number of HIV-RNA copies and CD4, the output data in the above graph.

5) Changes in tropism

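### Starting CD4 and HIV-RNA are collected but stratify no listed table, so differences in starting disease state can be read as effects of other factors

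*SAP*

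**What the plan says.** Protocol 7.7 collects, on one line, "Date of test, number of HIV-RNA copies, CD4 count, CDC classification, body weight and tropism". Protocol 8.2 sets two factor-finding aims. For safety, "factors affecting the onset of ADRs will be also examined". For efficacy, the parameters, CD4 and HIV-RNA among them, "will be tabulated and analyzed by patient background characteristic to examine factors affecting the efficacy of Celsentri". Protocol 7.10(i) makes immune competence the first priority item because "concern that Celsentri may affect immune competence (onset of infections, malignancies, etc". Of these events it says that "they will be tabulated by the causal relationship with Celsentri and stratified according to patient background characteristics".

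The SAP turns two of the variables in Protocol 7.7 into baseline items under Handling of items: CDC class before administration and tropism at first administration. CD4 and HIV-RNA get no such item. The adverse reaction incidence table under Table 3 ends its list of factors with "CDC classification of severity prior to administration, tropism classification at the first administration, concomitant treatment, blood coagulation factor"; CD4 and HIV-RNA stand nowhere in that list. In Table 4, CD4 and HIV-RNA are outcomes only, charted for all patients and "in patients with and without treatment history, with and without concomitant CYP3A inhibitors, sex, with and without complications, with and without concomitant drugs, CDC classification".

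On testing, the SAP's General Definitions name the chi-square test, with Fisher's exact test added at one degree of freedom. No adjusted or multivariable analysis is named.

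**The concern.** There is no comparator, so the survey learns by comparing strata of treated patients with each other. Such a comparison is only as good as the similarity of the strata at the start.

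- **Efficacy.** A patient below the assay limit at Month 0 cannot show a fall in HIV-RNA. The fall read from a stratum therefore depends on its share of such patients as well as on the drug. Treatment history does not isolate them: the SAP sets it to present for any earlier anti-HIV drug, which pools suppressed and viraemic patients. Some patients may also be on Celsentri already at Month 0. Protocol section 3 admits retrospective patients, and the SAP resets a start date before approval to the approval date.
- **Safety.** If infection risk rises as CD4 falls (an assumption here, though a natural one for a question about immune competence), a factor that is more common among patients with low CD4 will show more infections whether or not it has any effect.

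At stake is the survey's main product: a list of factors that seem to affect safety or efficacy, and the decision whether a further study is needed.

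**Working it through.** **1. Check of the lists.** The plan states no sample size calculation, power or effect size on this point, so there is no figure to reproduce. The check is whether starting CD4 or HIV-RNA appears anywhere as a background item or stratum.

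| Place in the SAP | Starting CD4 | Starting HIV-RNA | HIV-related items present |
|---|---|---|---|
| Handling of items | no | no | CDC class, tropism, treatment history, duration of disease |
| Table 2, patient composition | no | no | the same four |
| Table 3, adverse reaction incidence | no | no | the same four |
| Table 3, reactions/infections list | no | no | the same without tropism |
| Table 4, HIV-RNA/CD4 charts | outcome only | outcome only | treatment history, CDC class |

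The CDC strata are A, B, C and P-0 to P-2, with no CD4 bands.

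**2. Efficacy illustration (all inputs assumed).** Let d be the log10 fall in viraemic patients, the same in both strata, with no change in suppressed patients. Let s be the share suppressed at Month 0. The mean change is (1 − s) × (−d), so the gap between two strata is (s1 − s0) × d. The log10 scale is also an assumption; the SAP does not specify one.

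| s1 and s0 | gap, d = 1.5 | gap, d = 2.5 |
|---|---|---|
| 20% and 0% | 0.3 | 0.5 |
| 50% and 10% | 0.6 | 1.0 |
| 70% and 10% | 0.9 | 1.5 |

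Example: 0.5 × (−2.5) = −1.25 and 0.9 × (−2.5) = −2.25, a gap of 1.0 log10 with no true difference.

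**3. Safety illustration (all inputs assumed).** Let R be the risk ratio of infection for low against higher CD4, and p1 and p0 the shares with low CD4 in the two groups of a factor with no effect. Crude risk ratio = [1 + p1(R − 1)] / [1 + p0(R − 1)]. With p0 = 20%:

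| p1 | R = 2 | R = 3 | R = 5 |
|---|---|---|---|
| 30% | 1.08 | 1.14 | 1.22 |
| 40% | 1.17 | 1.29 | 1.44 |
| 50% | 1.25 | 1.43 | 1.67 |
| 60% | 1.33 | 1.57 | 1.89 |

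**4. Chance of a false flag.** Take 5% risk at higher CD4 and shares of 50% and 20%. Group risks are 7.5% and 6% (R = 2), 10% and 7% (R = 3), 15% and 9% (R = 5). By the normal approximation, a two-sided 5% test is significant in the direction of the gap 6%, 12% and 26% of the time with 100 patients per group, and 9%, 19% and 46% with 200. The nominal rate in that direction is 2.5%.

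**The case against.** The strongest reply is that the plan already shows part of what is asked for.

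- **Month 0 is shown.** The Table 4 charts plot test values, so each stratum's starting level appears, and a companion listing gives each patient's results by time point. A reader might infer that baseline imbalance would go unseen. For efficacy it would not. But seeing an imbalance does not separate it from the factor, and no safety table has such a display.
- **Proxies exist.** CDC class and treatment history are in both the safety and the efficacy tables. This stands in part; a separate CDC row does not adjust any other row.
- **Causality comes first.** The Table 3 incidence table and reactions/infections list count only events that the company cannot rule out as related. A reader might infer that HIV-driven infections flow straight into them. The documents do not support that: the company's assessment may remove some. Protocol 7.10(i), however, promises adverse events tabulated by causality, not only adverse reactions.
- **Case mix and effect sizes are not documented.** The documents do not say how many patients start suppressed, failing or untreated. This stands; every size above is conditional.
- **The aim is screening.** True, but screening by factor is where an unadjusted imbalance produces false leads.
- **Unseen mock-ups may list CD4.** A line listing would still not be a stratified table.

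**Conclusion.** The omission is certain from the text: starting CD4 and HIV-RNA are neither background items nor strata in any listed table. With one-factor comparisons and no adjustment, differences in starting disease state can be read as effects of other factors. A reader might go further and conclude that they will be, or that the planned tables are invalid. The documents support neither, since they give no baseline distribution and no effect sizes.

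On the assumed inputs, a factor with no effect could show a gap of 0.3 to 1.5 log10 in HIV-RNA fall (true fall 1.5 to 2.5 log10 if viraemic, none if suppressed) or a crude risk ratio of 1.08 to 1.89 (2- to 5-fold infection risk at low CD4). The safety figure applies to infection adverse events before any causality filter; for the planned adverse reaction tables it could be smaller. The change is worth making because the raw values are already collected and the aims depend on them.

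**What to change.** 1. **Efficacy charts (Table 4).** Add Month 0 HIV-RNA as a stratum with one cut-off for all years and sites, and show the other factor charts within the two groups. The cut-off must be fixed because the detection limit in the SAP changes by period and site (substituted values 399, 39 and 19). Below 400 copies is one option: the substitution rule already uses that boundary, and all three values fall under it. Read maintenance in the suppressed group and fall in the other.
2. **Safety (Tables 2 and 3).** Derive Month 0 CD4 for the safety group with the window that General Definitions sets for values before administration. Add it, with an unknown row, to the patient composition table, the adverse reaction incidence table and the reactions/infections list. Label these one-way rows as descriptive; they do not adjust the other rows.
3. **Priority item 7.10(i).** Tabulate infection and malignancy adverse events by causality and coarse CD4 band (for example <200, ≥200, unknown), with the key background factors shown within band. This cross-classification is what addresses the confounding.

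**Cost.** No new data. The SAP derives Month 0 values only for the efficacy group, so the safety group needs one extra derivation, and 7.10(i) needs one additional table. Cells will be small, and the unknown row may be large, because patients without CD4 or HIV-RNA values around administration leave the efficacy group but stay in the safety group.

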5.2 Patient Enrollment

(1) For patients who have been on drugs subject to the HRD cooperative investigation at the time of the contract or will start to receive them during the survey period, the investigator/subinvestigator should enter required information (medical record number or identification number, patient's initials [as necessary], gender, birth date [as necessary, age; e.g., age group], pregnancy status, inpatient/outpatient status, name of the drug surveyed and start date of treatment) on the enrollment screen of the EDC system, and send it using the user's ID and password issued for each investigator/subinvestigator. The patients' enrollment numbers will be issued by the EDC system. The sites that cannot connect to the external network should send or collect the data after inputting them in the SPC.

Patients who have been continuously on the drugs subject to the HRD cooperative investigation will be automatically continued to be enrolled based on data of the previous CRFs.

(2) The CRO should, as necessary, report the status of patient enrollment to the applicable companies using an HRD cooperative investigation control chart.

(3) Sites having a markedly high number of patients should first understand an expected number of new patients and then enroll new patients in the order of the re-enrollment of new patients on the day of enrollment in the HRD cooperative investigation among continuing patients and patient verification by the sites. The ratio of the number of re-enrolled continuing patients and newly enrolled patients should be adjusted. Overall, approximately 40 patients per investigator should be enrolled.

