For the patients who underwent a tropism assay (the patients whose tropism had been classified when the administration was started), prepare a list of their tropism assay results obtained within ±45 days of each point at Month 3, 6, 9, etc. of administration.

NOTE: These table forms may be subject to change due to the aggregated results or the relevant system.

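### The HIV-RNA/CD4 chart does not require values to be taken on CELSENTRI and plots raw means over a changing set of patients, so it is unclear what the curve represents

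*SAP*

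**What the plan says.** The chart rule is in the SAP under Type of Tables, 4) Table for patients in the efficacy analysis group.

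- **Baseline:** "Pre-administration (Month 0) should be the most recent date within 30 days before administration including the first administration date".
- **Later points:** the instruction that begins "For post-administration (Month 3, 6, 9, etc" is to "choose the value obtained on the most recent date within ±45 days from each point of Month 3, 6, 9, etc".
- **Axis:** test values are plotted against "months after administration (for every 3 months) on the x-axis".
- **Missing values:** if a test value is "missing either before or after administrations, it should not be included in the chart".
- **Sparse points:** a point with one patient is shown as an unconnected dot. A companion listing gives the patient numbers and results at each point.

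The efficacy group (SAP, Handling of cases) is the safety group minus patients treated outside the indication and patients lacking CD4/RNA data around administration. It sets no condition on being on drug.

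Elsewhere the SAP does separate time on drug. Administration period and total dose leave out washout, concomitant drugs count only if used in the CELSENTRI administration period, and a continued/suspended status is derived (SAP, Handling of items).

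On follow-up, Protocol 5.2(1) says that patients continuously on any drug covered by the joint survey "will be automatically continued to be enrolled based on data of the previous CRFs". Protocol section 9 describes a common CRF, which may be completed once per patient even when several anti-HIV drugs are given together.

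The tropism list (SAP, Type of Tables, 5) uses the same ±45-day windows, "at Month 3, 6, 9, etc. of administration".

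**The concern.** Two features make the curve hard to interpret.

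**Off-drug values are not excluded.** A patient who leaves CELSENTRI for another survey drug can remain in the joint survey and go on supplying HIV-RNA and CD4 results. As written, the chart rule would accept them.

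**The patients differ between points.** The chart shows raw test values rather than change from baseline, and the patients with a value vary by month. A rise or fall between Month 0 and a later point can therefore come from who is left rather than from any change within patients.

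Protocol 8.2(2) wants these parameters used to examine factors affecting the efficacy of Celsentri. The SAP splits the same chart by several background factors, so both problems carry into the subgroup curves. One split, with and without concomitant drugs, uses a label defined on CELSENTRI time, while the plotted values need not be.

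**Working it through.** The plan states no stopping rate, sample size or precision for this chart, so there is no figure of its own to reproduce.

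**1. Do the windows refer to dosing?** With the SAP's 30-day month, the windows are days 45–135 (Month 3), 135–225 (Month 6), 225–315 (Month 9) and 315–405 (Month 12). They tile the calendar and do not end at the final administration date.

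**2. How far can the axis run?** From approval (December 25, 2008) to data lock (March 26, 2018) is 3,378 days. 3,378 / 30 = 112.6 months and 3,378 / 90 = 37.5, so there are at most 37 three-month points. A patient starting on the last enrolment day (March 31, 2017) has 360 days to lock, or 12 months. Follow-up is therefore very uneven by design. These are outer limits, because results are entered yearly.

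**3. How large could the off-drug share be?** Two inputs are assumed: the proportion d stopping per year, and the share r of stoppers who still contribute values.

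- Off-drug proportion at month m: off = 1 − (1 − d)^(30m/365)
- Off-drug share of plotted values: off × r / (1 − off + off × r)

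| d per year | r | Month 12 | Month 24 | Month 60 |
|---|---|---|---|---|
| 5% | 1 | 4.9% | 9.6% | 22.3% |
| 5% | 0.5 | 2.5% | 5.1% | 12.6% |
| 10% | 1 | 9.9% | 18.8% | 40.5% |
| 10% | 0.5 | 5.2% | 10.4% | 25.4% |
| 20% | 1 | 19.8% | 35.6% | 66.7% |
| 20% | 0.5 | 11.0% | 21.7% | 50.1% |

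If the rate is instead a constant hazard h, then off = 1 − exp(−ht). At t = 2 years this gives 10%, 18% and 33% with r = 1. With r = 0.5 it gives 5%, 10% and 20%; for h = 0.20, 0.165 / (0.670 + 0.165) = 0.197. With r = 0 the share is zero at every point.

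**4. Can composition alone move the mean?** Suppose 70% of patients have a constant CD4 of 500 and stop at 5% per year, and 30% have a constant 250 and stop at 40% per year, with stoppers leaving the chart. With t = 30m/365, the plotted mean is

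(0.7 × 0.95^t × 500 + 0.3 × 0.60^t × 250) / (0.7 × 0.95^t + 0.3 × 0.60^t)

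It goes 425.0, 446.5, 463.1, 489.4 at Months 0, 12, 24 and 60, although no patient changes. The mean paired change would be zero throughout. These values are assumed, not trial data.

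**5. What does an on-drug restriction leave?** The off-drug share becomes zero, but the set shrinks. The share of baseline patients still plotted at Months 12/24/60 is 95.1/90.4/77.7% (d = 5%), 90.1/81.2/59.5% (d = 10%) and 80.2/64.4/33.3% (d = 20%). The restriction therefore does not cure the changing-set problem.

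**The case against.** A reader might infer that later points do mix in successor regimens, that suppression on those regimens is credited to CELSENTRI, and that the curve is flattered. The documents do not support that.

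- **Presence is not shown.** Staying enrolled in the joint survey does not prove that results from after CELSENTRI stopped reach this analysis. CRF copies go to the applicable companies, and line lists come from a CELSENTRI database whose content rules are not given. Only the possibility is established.
- **Direction is not shown.** Off-drug values could include treatment gaps and be worse, and patients who stop need not be failing.
- **The two mechanisms compete.** A stopper who keeps contributing is not lost, and one who is lost does not contaminate. The r = 1 figures are upper bounds for the assumed rates.
- **Each plotted patient should have a baseline.** On its natural reading, the missing-value rule makes later points subsets of the Month 0 patients. A stricter reading, dropping anyone with any missing later value, would fix the cohort, but it fits poorly with the single-patient rule and with enrolment running to March 2017.
- **The time origin is inferred.** Only Month 0 is tied explicitly to the first administration date. The tropism wording could mean time on drug.
- **Some information is already required.** The per-point listing lets n and paired changes be derived, and the table mock-ups are not in the text, so it cannot be said that n is not printed.
- **The survey is descriptive.** It has no comparator, and no test is specified for this chart. Using values regardless of treatment is legitimate if labelled.

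All of this stands and limits the claim. It does not supply the missing statement of which values the curve represents.

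**Conclusion.** The point holds as a gap in the written rule. Values from after CELSENTRI stops can enter the chart, and raw means are compared across patient subsets that differ by month.

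The size is unknown. Under assumed stopping of 5% to 20% per year, the off-drug share at year 2 is about 10% to 33–36% if every stopper contributes, and about 5% to 20–22% if half do. The upper ends depend on whether the rate is a hazard or an annual proportion. The share is nil if no stopper contributes.

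It would go too far to say that the curve is biased in CELSENTRI's favour, or that restricting it to on-drug values yields an unbiased one. The restriction removes contamination but leaves out patients who stopped, possibly for failure. For the tropism list, which has no mean or curve, only the on-drug or off-drug status of each result is at issue.

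**What to change.** In SAP Type of Tables, 4):

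1. State the time origin of the later points, and show two labelled curves: all values, and only values dated within the CELSENTRI administration period already derived, leaving out gaps.
2. Print n and n on drug at every point.
3. Plot the mean paired change from Month 0 for the patients contributing at that point. This compares the same patients within a point, not across points.
4. State that the on-drug curve is still subject to selective loss of patients who stop, so neither curve alone should be read as the drug's effect.

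In 5), flag each tropism result as on or off drug.

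The cost is SAP wording, a date filter on dates already held, and some extra output. No new data are needed. The downside is fewer patients at later months on the on-drug curve. Keeping the all-values curve means that nothing now planned is lost.
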